Study Treatment Groups:	Enrolled subjects will receive treatment at a 3.0mm depth and 0.30 J of energy. Treatment will be delivered in a 3 x 4 grid, 12 treatment squares, delivering 60 lines of treatment per square, i.e., 720 lines per axilla in each treatment (1440 lines total per treatment.)
Subject Population:	Adults between 18 - 75 years of age who meet the inclusion/exclusion criteria.
Inclusion Criteria:	
 1. Male or female, age 18-75 years. 2. Subject in good health. 3. Diagnosis of bilateral axillary hyperhidrosis refractory to previous topical therapies. 4. At least 50 mg of spontaneous resting axillary sweat production in each axilla measured gravimetrically at room temperature/humidity (20 - 25.6°C/20-80%) over a period of 5 minutes. (Patients should be at rest for at least 30 minutes after physical exercise including walking.) 5. HDSS score of 3 or 4. An attempt will be made to approximate an equal number of scores 3 and 4. 6. Understands and accepts the obligation not to undergo any other procedures in the areas to be treated through the follow-up period. 7. Willingness and ability to comply with protocol requirements, including returning for follow-up visits and abstaining from exclusionary procedures for the duration of the study. 8. Subjects of childbearing potential must have a negative urine pregnancy test result and must not be lactating at the Screening Visit and be willing and able to use an acceptable method of birth control (e.g. barrier methods used with a spermicidal agent, hormonal methods, IUD, surgical sterilization, abstinence) during the study. Women will not be considered of childbearing potential if one of the following conditions is documented on the medical history: 
 a. Postmenopausal for at least 12 months prior to study; b. Without a uterus and/or both ovaries; or c. Bilateral tubal ligation at least six months prior to study enrollment. 9. Absence of physical or psychological conditions unacceptable to the investigator. 10. Willingness to refrain from use of aspirin, Ibuprofen, Naproxen or any other NSAID, and Vitamin E in the 2 weeks prior to each study treatment . 11. Willingness and ability to provide written informed consent prior to performance of any study-related procedure.
Exclusion Criteria:	
 1. Dermal disorder including infection at anticipated treatment sites in either

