2.2 TYPE AND DESIGN OF STUDY

This study is a prospective, multi-center, non-randomized clinical trial. Up to 20 subjects who are naïve to Ultherapy for treatment of hyperhidrosis will be enrolled if all entrance criteria are met confirming eligibility for study treatment. Subjects will be treated using the Ulthera® System by the study investigator, sub-investigator or delegated clinician, receiving treatment in a 3 x 4 grid, 12 treatment squares, 60 lines of treatment per square, at one treatment depth (3.0mm), at 0.30 J of energy.

Ultrasound images will be captured of each axilla prior to the first study treatment to assess dermal thickness and depth of sweat glands. A gravimetric measurement of sweat production, starch iodine test, and pregnancy screening test, if applicable, will be performed prior to each study treatment. Digital images of the starch iodine test will be obtained. HDSS scores will be obtained prior to each treatment. During treatment, the average Numeric Rating Scale (NRS) score will be obtained by axilla treated.

Following the completion of study treatment(s), follow-up visits will be at 30, and 90 days post-treatment to assess safety and efficacy. Gravimetric sweat production measures and starch iodine tests will be completed at treatment visit #2 and at all follow-ups for all study groups. Digital images of the starch iodine test will be obtained. HDSS scores will be obtained at the treatment visit(s) and at all follow-ups for all study groups.

Efficacy will be determined by HDSS score reduction from a 3 or 4 at baseline to a 1 or 2 at 30 days post-treatment. Subject Gravimetric results, Starch iodine results, and HDSS scores at all follow-ups will also be analyzed as secondary outcomes.

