4.5 SUBJECT RANDOMIZATION AND TREATMENT GROUP ASSIGNMENT

Subjects are not randomized in this study. They will all be treated using the same treatment approach (see Section 5.1 for Study Treatment details).

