5.3.1 PRIMARY ENDPOINT

The primary endpoint of this study is HDSS score reduction from a 3 or 4 at baseline to a 1 or 2 at 30 days post-treatment #2.

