5.6 WITHDRAWAL CRITERIA AND PROCEDURES

All subjects have the right to withdraw at any point during the study without prejudice. The investigator can discontinue any subject, at any time, if medically necessary. The reason for subject's withdrawal should be documented on the appropriate study-specific data form. The subject must undergo the recommended follow-up assessments specified for the last study visit unless contraindicated due to a medical condition. Withdrawn subjects will not be replaced.

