6. STATISTICAL ANALYSIS

For a given parameter, data will be summarized for each time point for which data for that parameter are available. Summaries will be displayed by time point. Subjects with incomplete data will be included in summaries for which they have data available. Baseline will be defined as the most recent observation before the first treatment. Categorical variables will be summarized as frequencies and percentages in each category. Continuous and ordinal variables will be summarized as numbers of subjects, means, standard deviations, medians, and ranges. For the primary efficacy outcome, two-sided 95% confidence intervals will be calculated for differences in proportions between study groups. All programs for data output and analyses will be written in SAS® version 9.2 or higher (SAS Institute, Inc., Cary, NC).

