6.1 EFFICACY ANALYSIS

The primary analysis of efficacy will be based on the evaluable treated subjects, hence, only those subjects who received a complete or partial study treatment and completed a follow-up visit at 30-days post-treatment #2 will be included in the analysis using the Last Value Carried Forward method. Analyses of safety will include all subjects who received (complete or incomplete) study treatment.

Efficacy will be the proportion of treated subjects determined to be improved by the reduction in the number of sweat glands from baseline to 30-days post-treatment #2.

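### The 95% confidence interval planned for the primary outcome compares study groups, but the trial has one group, so the HDSS responder proportion has no usable interval

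*Combined protocol and SAP*

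**What the plan says.** Section 6 plans counts and percentages for categorical variables and then adds one inferential statement for the primary efficacy outcome: "two-sided 95% confidence intervals will be calculated for differences in proportions between study groups". It is the only interval in the plan.

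The design sections describe a single group. The Study Treatment Groups entry of the synopsis gives one regimen: "Enrolled subjects will receive treatment at a 3.0mm depth and 0.30 J of energy". Section 4.5 says that subjects are not randomized and that "They will all be treated using the same treatment approach". Section 2.2 calls the trial non-randomized and gives the same regimen, yet twice speaks of groups in the plural: "HDSS scores will be obtained at the treatment visit(s) and at all follow-ups for all study groups" and "starch iodine tests will be completed at treatment visit #2 and at all follow-ups for all study groups". It does not define any such groups.

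On the outcome itself, Section 5.3.1 states: "The primary endpoint of this study is HDSS score reduction from a 3 or 4 at baseline to a 1 or 2", assessed 30 days after the second treatment. Section 6.1 instead describes efficacy as the proportion of treated subjects "determined to be improved by the reduction in the number of sweat glands" over the same period.

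Section 6.1 limits the primary analysis to evaluable treated subjects, and Section 5.6 says "Withdrawn subjects will not be replaced".

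**The concern.** A difference in proportions needs two proportions, and this design produces one. If no second group exists, the only inferential statement attached to the primary outcome cannot be carried out, and the plan is silent on the interval that could be: one for a single responder proportion.

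What is at stake is the stated precision of the main result. In a 20-subject pilot, a bare percentage says little about which response rates the data can exclude. Without a replacement, the interval would have to be chosen after the data are seen or left out. Section 6.1 adds to the gap because the analysis section describes a different quantity from the endpoint section, so the plan does not consistently identify the proportion to which an interval would attach.

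**Working it through.** **Step 1: look for a second group.** The plan states no interval width, power or sample-size derivation for this trial, so there is no figure of its own to reproduce. The first check is whether any reading gives the Section 6 sentence two groups.

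- *A control, sham or second regimen.* None is described. The synopsis, Section 2.2 and Section 4.5 all give one regimen for everyone.
- *Baseline HDSS 3 versus baseline HDSS 4.* Inclusion criterion 5 aims for roughly equal numbers, but only as an enrolment goal. These subsets are never called study groups, and the difference between them would not estimate the overall response.
- *Baseline versus follow-up.* These are time points, not groups. Every subject must enter with a score of 3 or 4, so the responder proportion at baseline is 0 by design.
- *The earlier hyperhidrosis pilot (Section 1.6.5).* This had 12 active and 8 sham subjects. Its 67% corresponds to 8/12, and the two-sided Fisher exact test of 8/12 against 0/8 gives p = 0.0047, which agrees with the reported 0.005. It is the only HDSS responder comparison between groups in the document, and it belongs to another study.

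None of these supplies a second study group for this trial.

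**Step 2: see what else covers the primary outcome.** Section 6 otherwise offers frequencies and percentages. Section 6.1 gives a proportion with no interval, method or threshold. Nothing fills the gap.

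**Step 3: compute what a single-proportion interval would show.** Inputs:

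- n = 20 treated subjects (synopsis).
- Response between 50% and 70%. This is an assumption, set around the earlier pilot's 67%.
- n = 16 evaluable. This is also an assumption: 20% of 20 not evaluable, 20 − 4 = 16.

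For x responders out of n, the exact (Clopper-Pearson) limits are

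- lower = 2.5% quantile of Beta(x, n − x + 1)
- upper = 97.5% quantile of Beta(x + 1, n − x)

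| Responders | Proportion | Exact 95% interval | Width (points) |
|---|---|---|---|
| 10/20 | 50.0% | 27.2% to 72.8% | 45.6 |
| 13/20 | 65.0% | 40.8% to 84.6% | 43.8 |
| 14/20 | 70.0% | 45.7% to 88.1% | 42.4 |
| 8/16 | 50.0% | 24.7% to 75.3% | 50.6 |
| 11/16 | 68.8% | 41.3% to 89.0% | 47.7 |

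**Step 4: see how much the method matters.** With p = x/n and z = 1.96, the Wilson limits are

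(p + z²/2n ± z·√[p(1 − p)/n + z²/4n²]) / (1 + z²/n).

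For 13/20: z² = 3.84, z²/2n = 0.096 and 1 + z²/n = 1.192. The centre is (0.65 + 0.096)/1.192 = 0.626. The half-width is 1.96 × √(0.011375 + 0.002401)/1.192 = 0.193. The interval is 43.3% to 81.9%, against 40.8% to 84.6% for the exact method. Each limit moves by less than 3 points, so the choice of method matters far less than having an interval at all.

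**The case against.** The strongest reply concerns weight. This is a small pilot with no hypothesis test, comparator or success threshold. The responder count will be reported, and any reader can derive an interval from it. Section 6 already fixes the sidedness and the 95% level, so only the single-proportion method is open, and Step 4 shows that this matters little. The widths above come from the sample size, not from the faulty sentence, and would be the same under a correct plan. The 67% anchor comes from a different regimen that used two transducers.

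Much of that is fair. It limits the seriousness of the point and means that the table shows what the corrected plan would report, not an error in an estimate. It does not rescue the sentence: an analysis named for the primary outcome still cannot be run, and a pilot's main use is to estimate response with its uncertainty.

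A second reply is that the sweat gland wording in Section 6.1 is a separate matter, because the synopsis, Section 2.2 and Section 5.3.1 all point to HDSS and no scheduled post-treatment assessment counts glands (Table 3.1-1 lists axillary ultrasound images only at screening). HDSS is indeed the evident intention. Even so, the section that governs the analysis names something else, and the interval cannot be specified cleanly until the two agree.

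A third is that Section 6.1 both requires the 30-day visit and invokes carrying the last value forward, which leaves the denominator open to question. That is true and needs its own clarification, but it does not make a single-proportion interval unsound.

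**Conclusion.** The concern holds. The planned interval for the primary outcome cannot be calculated in a one-group trial, and the HDSS responder proportion has no specified interval. This is a reporting gap, not a bias: the count and percentage are unaffected, and no stated decision rule depends on the interval.

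The precision left unstated is about 42 to 46 percentage points of interval width with 20 subjects, and about 48 to 51 points with 16. These figures assume a response of roughly 50% to 70% and, for the second range, that 4 of 20 subjects are not evaluable. The conclusion that the interval cannot be calculated needs neither assumption. The sentence should be corrected before the data are analysed.

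**What to change.** Replace the sentence in Section 6 with wording such as:

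> *For the primary efficacy outcome, the proportion of HDSS responders among evaluable treated subjects (Section 6.1) will be presented with a two-sided 95% Clopper-Pearson confidence interval for a single proportion. A responder is a subject who enters with a score of 3 or 4 and scores 1 or 2 at the visit 30 days after treatment #2.*

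Wilson would serve equally well; what matters is that one method is named in advance.

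Two consequential edits follow. Remove the references to multiple study groups in both places in Section 2.2. Reword the efficacy sentence in Section 6.1 so that it describes the HDSS endpoint of Section 5.3.1.

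The cost is one replaced sentence, two short deletions and one aligned sentence, with no new data, visits or procedures. The only drawback for the sponsor is that the report will show a wide interval.

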6.1 EFFICACY ANALYSIS

The primary analysis of efficacy will be based on the evaluable treated subjects, hence, only those subjects who received a complete or partial study treatment and completed a follow-up visit at 30-days post-treatment #2 will be included in the analysis using the Last Value Carried Forward method. Analyses of safety will include all subjects who received (complete or incomplete) study treatment.

Efficacy will be the proportion of treated subjects determined to be improved by the reduction in the number of sweat glands from baseline to 30-days post-treatment #2.

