3. STUDY PROCEDURES

3.1 SCHEDULE OF ASSESSMENTS AT EACH STUDY VISIT

Table 3.1-1 provides an overview of the subject screening procedure, baseline evaluation, treatment plan, and follow-up requirements.

TABLE 3.1-1 SCHEDULE OF ASSESSMENTS

Evaluation	Screening ⁺	Baseline / Treatment #1 ⁺ Day 0	Telephone Contact Day 7±2D Post-Treatment #1	Treatment #2 Day 30±7	Telephone Contact Day 7±2D Post-Treatment #2	Follow-up Intervals Post Treatment #2	
						Day 30±7	Day 90±7
Screening and Subject Consent	√						
Initial Evaluation (Includes entrance criteria, eligibility assessment, demographics, medical history, clinician assessment)	√						
Pregnancy Screen	√ [^]	√ [^]		√ [^]			√
Study Treatment		√		√			
NRS for Subject Pain Assessment		√		√			
HDSS		√		√		√	√
Gravimetric Test	√			√		√	√
Starch Iodine Test and digital images of results		√		√		√	√
Obtain Axillary Ultrasound Images	√						
AE Forms	√	√	√	√	√	√	√

+Screening and Baseline/Treatment Visits may be separate visits or combined into one visit.

[^] Pregnancy:

- a. If a subject becomes pregnant after the Baseline visit and all study treatments have been completed, the subject should continue to be followed.
- b. If a subject becomes pregnant after the Baseline visit but before any study treatments, the subject should be exited from the study.
- c. If a subject becomes pregnant after the Baseline visit but before all study treatments have been completed, additional study treatments should be discontinued and the subject should continue to be followed.

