8. RISK ANALYSIS

8.1 POTENTIAL RISKS

This treatment modality was designed to inherently minimize the risk to the subject. However, ultrasound exposure with subsequent heating of the soft tissue could involve the risks listed in **Table 8.1.1** below:

TABLE 8.1.1 EXPECTED TREATMENT EFFECTS

Expected Treatment Effects	Duration
Bruising/Ecchymosis	Up to 3 weeks
Edema/Swelling	Up to 2 weeks
Erythema/Redness	Up to 1 week
Acute Pain	Immediate/momentary (while energy is being delivered) - 2 hours
Induration	Up to 12 weeks
Pruritus	Up to 2 weeks
Welting/Raised Areas of Edema	Up to 4 weeks
Skin Burn, Scarring, Change in pigmentation	Up to 8 weeks
Tenderness/Soreness/Pain/Sensitivity to Touch	Up to 3 weeks
/Muscle Twitching/Tingling/Paresthesia/Numbness	Up to 5 weeks
Reduced Range of Motion	Up to 3 weeks
Skin Peeling	Up to 2 weeks

Additional potential risks include: nerve injury, arterial blood spasm, change in axilla odor, and reduction of underarm hair growth.

The risks from lidocaine with epinephrine may include pain and discomfort from the injections, infection at the anesthetic site, lightheadedness, nervousness, mood change, tinnitus, blurred vision, vomiting, sensations of heat, cold or numbness, tremors, seizures, or unconsciousness. Additional uncommon side effects may include bradycardia, hypotension and cardiac arrest. Allergic reactions may appear as skin rashes, swelling or anaphylaxis.

Risk associated with a starch iodine test may include an allergic reaction to iodine solution or starch powder. No risks are anticipated from completion of a gravimetric sweat test or ultrasound imaging.

These risks will be minimized or reduced by monitoring the subject during the treatment and observing the skin's response to receiving the treatment. If the treatment is not tolerated, the investigator must stop administering treatment for the subject's safety, and the subject will be followed for adverse events for 90 days.

Previous clinical studies with the Ulthera® System have shown that the sensory response was tolerable from the subject's and investigator's perspectives. The discomfort was transient and no subject had any residual pain beyond 30 minutes.

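### Section 6.1 cannot be carried out as written: its outcome is a gland count nobody takes, its carry-forward rule has almost nothing to fill, and missing subjects leave the rate without a stated range

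*Combined protocol and SAP*

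**What the plan says.** Section 5.3.1 defines the primary endpoint as "HDSS score reduction from a 3 or 4 at baseline to a 1 or 2 at 30 days post-treatment #2". Section 2.2 and the synopsis agree.

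Section 6.1 sets out the primary analysis in three steps:

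- **Set.** "only those subjects who received a complete or partial study treatment and completed a follow-up visit at 30-days post-treatment #2 will be included".
- **Missing data.** The same sentence says these subjects "will be included in the analysis using the Last Value Carried Forward method".
- **Outcome.** The next paragraph reads: "Efficacy will be the proportion of treated subjects determined to be improved by the reduction in the number of sweat glands", from baseline to 30 days after treatment #2.

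For safety the set is wider: "Analyses of safety will include all subjects who received (complete or incomplete) study treatment".

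Subjects can leave before the 30-day visit in several ways. Section 5.6 allows withdrawal at any time and discontinuation by the investigator, without replacement. Section 5.7 covers loss to follow-up. Section 8.1 says "If the treatment is not tolerated, the investigator must stop administering treatment" and that "the subject will be followed for adverse events for 90 days". The footnote to the schedule in section 3.1 says that, for pregnancy between the two treatments, "additional study treatments should be discontinued and the subject should continue to be followed".

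**The concern.** The outcome sentence does not match the endpoint. A programmer following section 6.1 would look for a gland count at baseline and at 30 days and find neither.

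The missing-data sentence works against itself. It first removes everyone without the 30-day visit and then names a method whose usual purpose is to keep such people.

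Entry to the primary set also depends on attending the visit at which the endpoint is measured. A subject who never receives treatment #2 cannot have a visit 30 days after it. In a single-arm study of up to 20 subjects, each absence moves the rate by several points, and no control arm would show the shift. What is at stake is the meaning of the one headline proportion, and whether its definition is settled before the data are seen.

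**Working it through.** **Plan's own figures.** N = 20 is given without effect size, power or dropout, so there is nothing to reproduce. The hyperhidrosis pilot in section 1.6.5 reports 67% of 12 active subjects responding against none of 8 sham subjects. Fisher's exact test on 8/12 v 0/8 gives p = 0.0047, matching the stated 0.005. A rate of 13/20 = 65% is therefore a reasonable assumption for illustration, and no more than that.

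**(a) Outcome against schedule.** Section 5.4 lists the follow-up assessments as gravimetric test, starch iodine test and HDSS. Section 3.1 schedules axillary ultrasound at screening only, and section 2.2 gives its purpose as dermal thickness and gland depth. Starch iodine, per section 5.3, shows the area of efficacy. None of these counts glands, so the outcome in section 6.1 cannot be computed in any analysis set.

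**(b) LVCF against the set.** HDSS is taken at baseline, at treatment #2, and at 30 and 90 days. A value carried forward to day 30 could only be the baseline score, which is 3 or 4 by entry criterion and so always a non-response, or the treatment #2 score, which reflects one treatment. Within a set defined by attending the 30-day visit, the only gap left is a blank HDSS at an attended visit.

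The readings can differ. Assume 20 treated, 17 attending, 12 of those responding, and 2 of the 3 absentees scoring 1 or 2 at treatment #2:

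- evaluable only: 12/17 = 70.6%
- LVCF over all treated: (12 + 2)/20 = 70.0%
- all treated, missing as non-response: 12/20 = 60.0%

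**(c) Size of the possible error.** Let 20 be treated with 13 true responders, m missing, and r responders among the missing.

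- Evaluable rate = (13 - r)/(20 - m)
- Worst case, all missing as non-response = (13 - r)/20
- Best case, all missing as response = (13 - r + m)/20

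For m = 3, with errors in points against 65%:

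| r | Evaluable | Error | Worst case | Error | Best case |
|---|---|---|---|---|---|
| 0 | 13/17 = 76.5% | +11.5 | 65% | 0 | 80% |
| 1 | 12/17 = 70.6% | +5.6 | 60% | -5 | 75% |
| 2 | 11/17 = 64.7% | -0.3 | 55% | -10 | 70% |
| 3 | 10/17 = 58.8% | -6.2 | 50% | -15 | 65% |

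The evaluable error spans +3.4 to -1.8 for one missing, +7.2 to -3.9 for two, and +16.25 to -8.75 for four. It is zero for none. The worst-to-best range contains 65% in every row of the table.

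In expectation, with a separate assumed true rate of 60% and 15% missing overall:

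| Missing among responders / non-responders | Evaluable | Missing as non-response |
|---|---|---|
| 15% / 15% | 0.51/0.85 = 60.0% (0) | 51.0% (-9.0) |
| 5% / 30% | 0.57/0.85 = 67.1% (+7.1) | 57.0% (-3.0) |
| 20% / 7.5% | 0.48/0.85 = 56.5% (-3.5) | 48.0% (-12.0) |

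**Scale.** The Clopper-Pearson 95% interval for 13/20 is 40.8% to 84.6%, about 44 points wide.

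**The case against.** The strongest reply is that this is a small uncontrolled pilot with no test and no threshold, and that sampling error exceeds every shift shown above. That stands, and it limits how much the point matters.

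Several safeguards also exist. Section 6 asks for summaries by time point, with numbers of subjects for ordinal variables, so the baseline and 30-day counts should ordinarily appear. Section 5.7 requires contact attempts and a documented reason for discontinuation. Section 5.6 asks withdrawn subjects for the last-visit assessments, which include HDSS. What remains missing is a requirement to show these beside the primary result.

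On the gland wording, section 2.1 does state the objective as an effect on axillary sweat glands. That explains the phrase but does not supply a measurement. LVCF might have been meant for day 90, but the sentence concerns the primary analysis at day 30.

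Four stronger readings are tempting, and the documents support none of them:

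- *The evaluable rate is inflated.* No dropout rate or pattern is given, and the error can take either sign.
- *Stopping for intolerance removes a subject from efficacy.* Section 6.1 admits partial treatment, so someone who stops during treatment #2 and attends at 30 days stays in. Section 5.7 also wants all subjects followed to the end of the study, despite the narrower wording of section 8.1.
- *Section 6.1 uses two contradictory denominators.* The phrase in the outcome sentence can be shorthand for the evaluable treated subjects named just above it. It is ambiguous, no more.
- *Missing should count as non-response in the headline.* That rule is further from the truth in two of the three expectation scenarios. If 3 of 20 go missing at random, two or three of them are responders with probability (78 × 7 + 286)/1140 = 832/1140 = 73%, and in those cases the evaluable rate is nearer. Scoring subjects who never had treatment #2 as failures also changes the question from the effect of two treatments to the success of a planned course.

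**Conclusion.** The point holds as a defect of specification. The gland-count outcome conflicts with section 5.3.1 and cannot be computed. The LVCF clause is either nearly empty or contradicted by the inclusion rule in its own sentence. These two conclusions rest on the text alone.

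The analysis-set part is conditional. Subjects who withdraw, are discontinued, are lost or never receive treatment #2 drop out of the primary rate, which may then be biased upward, downward or not at all. The illustrated size of +11.5 to -6.2 points assumes 20 treated, 13 true responders and three missing, and none of these is a forecast. Because there is no threshold or comparator, the consequence is for how the rate is interpreted. It should be corrected before the data are analysed, but it does not undermine the study.

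**What to change.** Amend section 6.1 as follows:

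1. Replace the sweat-gland wording with the HDSS response of section 5.3.1.
2. Delete the LVCF wording.
3. State the primary denominator explicitly.
4. Beside the evaluable proportion (x/n), report the number treated, the reason for each missing subject, and an all-treated range from all missing as non-response to all missing as response. Pre-specify the non-response figure as a sensitivity bound, not the headline.
5. Add a supporting sensitivity analysis using HDSS collected at withdrawal under section 5.6, where available.
6. Show subjects who never received treatment #2 separately.

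The cost is a protocol amendment under section 15 and a little extra tabulation. Because it touches the primary analysis, it is unlikely to count as administrative and will probably need IRB or EC approval. No new data or visits are required.

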1.2 BRIEF AGING BACKGROUND AND TREATMENT OVERVIEW

Hyperhidrosis is a disease characterized by perspiration in excess of the physiologic amount necessary to maintain thermal homeostasis[1]. Hyperhidrosis can have very significant effects on patients' lives, causing physical discomfort and social embarrassment and negatively impacting occupational and daily activities.

[figure not shown]
Primary or idiopathic hyperhidrosis and secondary hyperhidrosis are the two main categories[2]. Patients can have excessive sweating either in a localized area (focal) or over the entire body (generalized). Primary disease is usually focal, affecting the soles, palms, and axillae in various combinations and with varying degrees of severity. Secondary hyperhidrosis can be generalized or focal. In secondary hyperhidrosis the symptoms are due to one of a large number of medical conditions, including endocrine disorders, neurological problems, use of certain drugs, cancer, chronic infections, dermatologic syndromes, and conditions associated with excess catecholamine discharge[3]. Occasionally hyperhidrosis can be seen on the head and face as a primary disorder or become apparent as gustatory sweating secondary to parotid surgery or diabetes. This study focuses on primary hyperhidrosis of the axillae.

Sweat glands in patients with hyperhidrosis are not histopathologically different from those in normal patients, nor is there an increase in the number or size of glands. The condition is caused by hyperfunction of the sweat glands rather than hypertrophy[4]. Patients with primary hyperhidrosis have a higher-than-normal basal level of sweat production as well as an increased response to normal stimuli such as emotional or physical stress.

Humans have up to four million sweat glands distributed over the body, of which about three million are eccrine sweat glands. Eccrine glands secrete an odorless, clear fluid that serves to aid in the regulation of body temperature by allowing heat loss by evaporation. Eccrine glands are in higher density on the soles of the feet and the forehead, followed by the palms and the cheeks.[5, 6] Apocrine sweat glands are located in limited areas—the axilla and urogenital regions—and produce a thick, odorless fluid that undergoes bacterial decomposition, leading to substances with strong odors. The ratio of apocrine to eccrine glands is one to one in the axillae and one to ten elsewhere.[5]

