4.6 STUDY IMAGES

Ultrasound images will be obtained of each axilla using the Ulthera® System at baseline. All starch iodine tests will be captured with digital images. All images will be captured using a 2D digital imaging system.

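### Section 6.1 bases efficacy on a fall in sweat-gland number, which no visit measures, instead of the HDSS primary endpoint, so the primary analysis as written cannot be run

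*Combined protocol and SAP*

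**What the plan says.** The second paragraph of Section 6.1 (Efficacy Analysis) makes efficacy the "proportion of treated subjects determined to be improved by the reduction in the number of sweat glands from baseline" to 30 days after the second treatment. It gives no counting method and no threshold.

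The endpoint sections name a different variable. Section 5.3.1 reads "The primary endpoint of this study is HDSS score reduction from a 3 or 4 at baseline to a 1 or 2", timed 30 days after the second treatment, and the synopsis agrees. Section 2.2 says "Efficacy will be determined by HDSS score reduction from a 3 or 4 at baseline to a 1 or 2", also at 30 days.

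On imaging, Section 2.2 says "Ultrasound images will be captured of each axilla prior to the first study treatment to assess dermal thickness and depth of sweat glands", and Section 4.6 confirms "Ultrasound images will be obtained of each axilla using the Ulthera® System at baseline". Section 5.4 lists the efficacy assessments at follow-up as gravimetry, starch iodine and HDSS.

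**The concern.** The analysis section and the endpoint sections describe two different quantities: an anatomical count and a patient-reported score. Only the score is collected. Section 6.1 holds the only definition of efficacy within Section 6. The opening of Section 6 refers to a primary efficacy outcome but does not say what it is, and never mentions HDSS.

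An analyst who follows Section 6 therefore has no computable primary result. An analyst who works around it must decide which section governs, and the plan is silent on that. In a 20-subject study in which everyone is treated alike (Section 4.5), there is no comparator. A responder definition fixed in advance is then one of the main protections against choosing the outcome after seeing the data.

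**Working it through.** The documents give no sample-size, power or alpha calculation for this trial, so there is no planned figure to reproduce. The check is a comparison of sections.

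**Step 1. Is gland number measured anywhere?**

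| Possible source | When | What it yields | Gland number? |
|---|---|---|---|
| Scheduled ultrasound (Sections 2.2 and 4.6, Table 3.1-1) | Once, before treatment #1 | Skin thickness, gland depth | No |
| Imaging during treatment (Section 5.1.4) | Treatments #1 and #2 | Coupling of transducer to skin | No |
| Starch iodine test (Section 5.3) | Baseline, treatment #2, 30 and 90 days | Area of sweating | No |
| Gravimetry (Section 5.3) | Screening, treatment #2, 30 and 90 days | Sweat weight per 5 minutes | No |
| Biopsy or histology | Not scheduled | – | No |

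The 6.1 proportion needs a baseline count, a 30-day count and a cut-off. None of the three exists:

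- subjects with a baseline gland count: 0 of 20
- subjects with a gland count 30 days after the second treatment: 0 of 20
- stated size of reduction that counts as improved: none

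**Step 2. Is the HDSS proportion computable?** Table 3.1-1 schedules HDSS at Baseline/Treatment #1 and at 30 days after the second treatment. The cut-off (3 or 4 falling to 1 or 2) is in Section 5.3.1. All 20 planned subjects are scheduled to have both values.

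**Step 3. What would the corrected analysis deliver?** For x responders among n evaluable subjects, the exact (Clopper-Pearson) two-sided 95% limits are

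- lower = the 2.5% point of Beta(x, n − x + 1)
- upper = the 97.5% point of Beta(x + 1, n − x)

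The responder counts below are assumptions, for illustration only. The earlier pilot in Section 1.6.5 reported 67% of 12 active subjects at the same time point.

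| x / n | Proportion | 95% limits |
|---|---|---|
| 5/20 | 25% | 8.7% to 49.1% |
| 10/20 | 50% | 27.2% to 72.8% |
| 13/20 | 65% | 40.8% to 84.6% |
| 15/20 | 75% | 50.9% to 91.3% |
| 12/18 | 66.7% | 41.0% to 86.7% |

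The intervals are wide, as expected with about 20 subjects, but each comes directly from data the trial already collects.

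**The case against.** The strongest reply is that the intended analysis is not in doubt. HDSS is named as the outcome in three places, with scale, cut-off and time point, and Section 6 already says categorical variables will be summarised as percentages at each visit. Read with Section 5.3.1, an HDSS responder percentage can be tabulated. A variable with no data also cannot be picked because its results look better, so outcome switching between these two definitions is unlikely. And this is a small non-randomised pilot with no hypothesis test or success threshold.

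Much of that stands. This is a correctable mismatch, not a loss of data. The likelier harm is a departure from 6.1 that has to be explained, or a proxy for gland number chosen late from the starch iodine or gravimetric results. What the reply does not do is make 6.1 executable: it works only by overriding the one efficacy definition in the statistical section.

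Two supporting arguments carry little weight. Section 1.2 says of hyperhidrosis "nor is there an increase in the number or size of glands", so gland count is not what marks the disease. But Section 1.3 proposes that the device damages glands, so fewer glands could still be a treatment effect. Likewise, the Section 2.1 objective about sweat glands does not in itself require a count. The finding needs neither.

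**Conclusion.** The concern holds and should be fixed before analysis. As written, the efficacy rule in Section 6.1 contradicts the declared primary endpoint and depends on a quantity that 0 of 20 subjects would have at either time point. The HDSS endpoint is scheduled for all 20 at both. This rests on the schedule of assessments being complete, and on Section 6.1 being current text, as it appears to be. The 0 of 20 shows that the stated rule cannot be computed; it does not measure bias or lost precision.

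**What to change.** Replace the second paragraph of Section 6.1 with wording to this effect: *Primary efficacy is the proportion of treated subjects in the primary analysis set who have an HDSS of 3 or 4 at baseline and of 1 or 2 at the 30-day visit after the second treatment.* Delete the reference to gland number. For consistency, bring the objective in Section 2.1 into line with the synopsis objective; this edit is secondary.

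The cost is a one-sentence amendment to 6.1 and a small edit to 2.1, with no added data, visits or subjects.

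Two neighbouring defects are separate, but are best settled in the same amendment because they also bear on the primary result. The first paragraph of 6.1 restricts the analysis to subjects who completed the 30-day visit yet applies Last Value Carried Forward. The opening of Section 6 plans an interval for a difference between groups, although Section 4.5 gives every subject the same treatment.
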